### **6.3 SENSITIVITY ANALYSES OF TIME TO LOSS OF SECONDARY PATENCY AND TIME TO LOSS OF PRIMARY PATENCY**

Several sensitivity analyses of the primary endpoint (time to loss of secondary patency) and key secondary endpoint (time to loss of primary patency) will be conducted. Each of these analyses will be conducted using the same statistical methodology as described in Sections 6.1 and 6.2. The sensitivity analyses are described below, in terms of the changes that will be made to the descriptions provided in Sections 6.1 and 6.2. Sensitivity analyses being conducted to exclude subjects from the [name] site are due to major GCP violations and data integrity concerns.

1. Exclude all subjects from the [name] site.
2. Treat death as an event, but censor for transplant, lost to follow-up, withdrawal due to non-compliance and voluntary withdrawal.
3. Exclude all subjects from the [name] site. Treat death as an event, but censor for transplant, lost to follow-up, withdrawal due to non-compliance and voluntary withdrawal.
4. Treat death, transplant, lost to follow-up, withdrawal due to non-compliance and voluntary withdrawal as an event.
5. Exclude all subjects from the [name] site. Treat death, transplant, lost to follow-up, withdrawal due to non-compliance and voluntary withdrawal as an event.

The results of all sensitivity analyses will be reported without adjustment for multiplicity.

## **6.4 TERTIARY EFFICACY ENDPOINTS AND ANALYSES**

No tertiary endpoints and/or analysis are planned for this study.

## **6.5 PROGNOSTIC FACTORS AND SUBGROUP ANALYSES**

No analyses based on prognostic factors are planned for the study. Sub-group analysis by geographic region (USA versus non-USA), gender, race (White; non-White), ethnicity (Hispanic or Latino; non-Hispanic or Latino) actual surgical location (upper arm; forearm), age group (<55; >=55 and <=70; >70), BMI (<30; >=30) will be performed. The subgroup analyses will be performed by repeating the statistical methods described above for loss of secondary patency and loss of primary patency for each subgroup, except that the models will be adjusted by the actual surgical placement location (upper arm, forearm). For example, the models will be performed including only male subjects, and then will be repeated including only female subjects.

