Unless otherwise specified, continuous variables will be summarized by presenting the number of non-missing observations, mean, standard deviation, median, inter-quartile range, minimum and maximum. Categorical variables will be summarized by presenting the number of subjects and percentage for each category.

Unless otherwise noted, all tests of treatment effects will be conducted at a 2-sided alpha level of 0.05 and two-sided 95% confidence intervals (CI) will be calculated. All tests of interactions between treatment groups and other factors will be conducted at a 2-sided alpha level of 0.10, unless otherwise noted. Parametric and nonparametric methods, as determined by the distribution of each variable, will be used to test statistical hypotheses of continuous variables. In the event of highly skewed data, a logarithmic transformation will be considered prior to any statistical testing.

All p-values will be rounded to 3 decimal places. A p-value rounded to 1.000 will be displayed as >0.999, and a p-value rounded to 0.000 will be displayed as <0.001.

Multiplicity will be managed by testing the primary and key secondary endpoints in a hierarchical fashion. All analyses will be performed using data pooled across sites.

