The hazard ratio (HAV relative to ePTFE graft) will be estimated using a Cox proportional hazards regression with treatment group and the surgical placement stratification variable as factors. Based on the estimated event-free rate in the ePTFE graft arm at the data cut-off using Kaplan-Meier method, the non-inferiority margin will be determined by the hazard ratio corresponding to a difference of 10 percentage points. Hazard Ratio (HAV to ePTFE) Margin = $\text{Log}(\text{ePTFE K-M estimated event free rate} - 0.1) / \text{Log}(\text{ePTFE K-M estimated event free rate})$ . For analyses conducted at 12 months, the hazard ratio will be calculated from the ePTFE K-M estimated event-free rate at 12 months. For analyses conducted at 18 months, the hazard ratio will be calculated from the ePTFE K-M estimated event-free rate at 18 months. Similarly, for analyses conducted at 24 months, the hazard ratio will be calculated from the ePTFE K-M estimated event-free rate at 24 months. If the upper limit of the two-sided 95% confidence interval for the hazard ratio is less than the corresponding non-inferiority margin hazard ratio, then non-inferiority will be demonstrated.

The primary analysis will be in the ITT analysis set. The analysis of the primary endpoints of interest will be repeated using the mITT and per-protocol analyses sets as confirmatory.

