- a. The RMST method will be used to evaluate non-inferiority of HAV versus ePTFE for all non-censored subjects in the trial reaching 18 months. We will utilize the 18-month (547.9 days) timepoint to calculate the mean survival times (loss of secondary patency) for each treatment group.
- b. The RMST method will be used to evaluate non-inferiority of HAV versus ePTFE for all non-censored subjects in the trial reaching 12 months. We will utilize the 12-month (365.25 days) timepoint to calculate the mean survival times (loss of secondary patency) for each cohort.
- c. The RMST method will be used to evaluate non-inferiority of HAV versus ePTFE for all non-censored FEMALE subjects in the trial reaching 24 months.
- d. The RMST method will be used to evaluate non-inferiority of HAV versus ePTFE for all non-censored MALE subjects in the trial reaching 24 months.
- e. The RMST method will be used to evaluate non-inferiority of HAV versus ePTFE for all non-censored FEMALE subjects in the trial reaching 18 months.
- f. The RMST method will be used to evaluate non-inferiority of HAV versus ePTFE for all non-censored MALE subjects in the trial reaching 18 months.
- g. The hazard ratio (HAV relative to ePTFE graft) will be estimated using a Cox proportional hazards regression at 24 months, with right-censoring of data occurring after 24 months (Day 730). Based on the estimated event-free rate in the ePTFE graft arm at the data cut-off using Kaplan-Meier method, the non-inferiority margin will be determined by the hazard ratio corresponding to a difference of 10 percentage points. Hazard Ratio (HAV to ePTFE) Margin = $\text{Log}(\text{ePTFE K-M estimated event free rate} - 0.1) / \text{Log}(\text{ePTFE K-M estimated event free rate})$ . If the upper limit of the two-sided 95% confidence interval for

the hazard ratio is less than the corresponding non-inferiority margin hazard ratio, then non-inferiority will be demonstrated.

- h. The hazard ratio (HAV relative to ePTFE graft) will be estimated for all FEMALE subjects using a Cox proportional hazards regression at 24 months, with right-censoring of data occurring after 24 months (Day 730).
- i. The hazard ratio (HAV relative to ePTFE graft) will be estimated for all MALE subjects using a Cox proportional hazards regression at 24 months, with right-censoring of data occurring after 24 months (Day 730).

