## 11 SAMPLE SIZE AND POWER CALCULATIONS

The original sample size calculation was based on the following assumptions:

For the primary endpoint of time to loss of Secondary Patency, the assumed 12-month event-free rates in the ePTFE graft is 60%. Based on 1:1 randomization, a 16-month enrollment period, and a 12-month follow-up period, a total sample size of 350 subjects will provide greater

- 90% power to demonstrate non-inferiority (with a 10% non-inferiority margin) if the 12-month event-free rate in the HAV arm is 66%
- 90% power to demonstrate superiority if the 12-month event-free rate in the HAV arm is 76%

For the key secondary endpoint of time to loss of Primary Patency, the assumed 6-month event-free rate in the ePTFE graft arm is 50%. Based on 1:1 randomization, a 16-month enrollment period, and a 12-month follow-up period, and under the assumption that the true 6-month event-free rate in the HAV arm is 55%, a total sample size of 350 subjects will provide greater than 90% power to demonstrate non-inferiority (assuming a non-inferiority margin of 10%). If the true rate in the HAV arm is as low as 53%, then there will be greater than 80% power to demonstrate non-inferiority.

During the course of the study a high enrolling site (~10% of total subjects) early terminated all of their remaining subjects and withdrew from study participation. The majority of these subjects had not yet had an event that would contribute to the primary endpoint analysis. To mitigate the potential loss of study power from this unexpected situation, the decision was made to extend the follow-up period for the primary and secondary efficacy analyses from 12 months post-implant to 18 months post-implant.

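### Subgroup non-inferiority is assessed by separate fits with no interaction test assigned, so at the planned effect identical results in men and women would give a pass in only one sex in about 47% of trials (even sex split)

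*SAP*

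**What the plan says.** SAP Section 6.5 lists seven subgroup factors: region, gender, race, ethnicity, actual surgical location, age group and BMI. For each it says: "The subgroup analyses will be performed by repeating the statistical methods described above for loss of secondary patency and loss of primary patency". Its example is that "the models will be performed including only male subjects, and then will be repeated including only female subjects".

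The method being repeated is that of Section 6.1. There "the non-inferiority margin will be determined by the hazard ratio corresponding to a difference of 10 percentage points", and the decision rule begins "If the upper limit of the two-sided 95% confidence interval for the hazard ratio is less than the corresponding non-inferiority margin hazard ratio"; when that condition is met, non-inferiority is declared.

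Section 6.1.1 adds eight sex-specific analyses. Items c to f call for a non-inferiority evaluation by RMST in women and men separately, at 24 and 18 months; item c reads "The RMST method will be used to evaluate non-inferiority of HAV versus ePTFE for all non-censored FEMALE subjects in the trial reaching 24 months". Items h to k only estimate a Cox hazard ratio by sex and state no decision.

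Section 4 gives a general rule: "All tests of interactions between treatment groups and other factors will be conducted at a 2-sided alpha level of 0.10". Neither 6.5 nor 6.1.1 names an interaction term, or says how to read a pass in one subgroup beside a non-pass in another. Section 6.5 also does not say whether a subgroup's margin comes from the overall ePTFE Kaplan-Meier rate or from the subgroup's own.

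**The concern.** Two separate tests, one per sex, do not compare the sexes. If one interval clears the margin and the other does not, the natural summary is that HAV is non-inferior in men but not in women, or the reverse. In a half-sample with moderate power, that pattern is common when the true effect is the same in both sexes. Sex is the factor singled out for repeated non-inferiority evaluation at 24 months, so a sex-specific reading of the results is foreseeable. The analysis that addresses the question, a test or estimate of interaction, has a level in the SAP but no assignment.

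**Working it through.** **Inputs.** SAP Section 11: 350 subjects, 1:1, 16-month enrolment, 12-month follow-up, ePTFE event-free rate 60% at 12 months, and "90% power to demonstrate non-inferiority (with a 10% non-inferiority margin) if the 12-month event-free rate in the HAV arm is 66" per cent. SAP Section 6.1: two-sided 95% interval, and about 20% deaths a year. SAP Section 4: interaction level 0.10. The documents give no sex share; I assume 50:50 and show the range to 70:30.

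**The plan's own power.** With exponential survival:
- true hazard ratio = ln 0.66 / ln 0.60 = 0.813
- margin = ln 0.50 / ln 0.60 = 1.357
- power = Φ[(ln 1.357 − ln 0.813) × √D / 2 − 1.96], where D is the number of events

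For 90% power, D = 4 × (1.960 + 1.282)² / 0.512² ≈ 161. Uniform 16-month accrual with at least 12 months of follow-up gives 185 events and 93.6% with no losses, or 158 events and 89.5% with 20% a year censored by death. The stated 90% is therefore reproduced to within a point once deaths are allowed for, although Section 11 does not list them as an input.

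**Power within each sex, same true effect and same margin.** At 90% overall power the expected z is 3.242. A share s of the events gives power Φ(3.242√s − 1.96). The chance that exactly one sex passes is p(1 − q) + q(1 − p).

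| Split | Power, larger group | Power, smaller group | Exactly one passes |
|---|---|---|---|
| 50:50 | 0.630 | 0.630 | 46.6% |
| 60:40 | 0.709 | 0.536 | 48.5% |
| 70:30 | 0.774 | 0.427 | 54.0% |

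At 93.6% overall power and an even split, each half has Φ(3.482/√2 − 1.96) = 0.69, and discordance is 2 × 0.69 × 0.31 ≈ 43%.

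**Dependence on the true effect.** Even split, range over six follow-up models: fixed 12, 18 or 24 months; 16-month accrual plus 12 or 18 months; and the last of these with 20% a year deaths.

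| HAV 12-month rate in both sexes | Exactly one sex passes |
|---|---|
| 50% (at the 12-month margin) | 3–5% |
| 60% (equal arms) | 37–44% |
| 63% | 47–50% |
| 66% (planned) | 41–50% |
| 70% | 18–39% |
| 76% (superiority scenario) | 1–12% |

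**Does the choice of margin matter?** The 46.6% uses one common margin. Simulating 3,000 trials per scenario with Cox models, 20% a year deaths, an even split and each sex's own formula margin gave 46% at 18 months and 45% at 24 months for the planned effect, and 39% and 41% for equal arms. The margin choice barely changes the result. These Cox figures only stand in for the RMST tests of items c to f.

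**The alternative.** With equal effects, one interaction test at 0.10 signals wrongly in 10% of trials by construction. At 161 events split evenly, the standard error of the log ratio of hazard ratios is 4/√161 = 0.315. Power is Φ(ln 2/0.315 − 1.645) ≈ 71% for a two-fold ratio and Φ(ln 1.5/0.315 − 1.645) ≈ 36% for a 1.5-fold ratio. Across seven factors, if independent, the chance of at least one false signal is 1 − 0.9⁷ = 52%.

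**The case against.** The strongest reply is that the plan draws no conclusion from subgroups. The fixed sequence in SAP Section 6.2 holds the primary test and three key secondary tests, none by subgroup, and multiplicity control covers only those. This stands: a reader might infer that the primary result is at risk, and it is not. It does not dispose of the point, because items c to f are written as non-inferiority evaluations by sex and 6.5 carries the decision rule over.

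Other limits also stand:
- A reader might infer opposite effects in men and women. The outcome counted is shown versus not shown, which is ordinary loss of power in part of the sample.
- A reader might infer that the SAP ignores interaction. It sets a level; what is missing is the assignment of a test to a factor.
- A reader might take near-half discordance as general. It falls to a few per cent if HAV performs very well or sits at the margin.
- A reader might count all eight sex-specific analyses as verdicts. Items h to k state none, unlike item g, which gives a margin and a rule.
- A reader might conclude that the sexes are definitely held to different margins. That is a fair reading of 6.5, but the text leaves it open.

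The interaction test has costs too: modest power, and an appreciable false-signal rate over seven factors.

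**Conclusion.** The concern holds in a limited form. The plan evaluates non-inferiority separately within subgroups and assigns no analysis that could tell a subgroup difference from low power. At the planned effect, 90% overall power and an assumed even sex split, equal true effects give a pass in exactly one sex in about 47% of trials, against a 10% false-signal rate for a single interaction test. The calculation rests on exponential survival, a common effect in both sexes, independent tests and a Cox approximation to the RMST items. It bears on how exploratory results are read, not on the confirmatory conclusion. It is worth correcting because the remedy is cheap and sex-specific statements are likely.

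**What to change.** In SAP Section 6.5, for each factor fit one Cox model with treatment, the factor, their interaction and placement location. For the location subgroup, use a single location variable, because actual and intended site would be nearly the same covariate twice. For items c to f of Section 6.1.1, report the difference between women and men in the RMST treatment difference, with its interval; a Cox interaction alone does not cover these items. Report each interaction at the 0.10 level already in Section 4, with subgroup estimates and 95% intervals. Label all of this exploratory and draw no non-inferiority pass or fail by subgroup.

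Applying the overall margin to every subgroup is not a substitute: the 46.6% was computed under a common margin.

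The work is a few model lines on data already collected. The costs are the loss of any pass/fail statement by subgroup, limited power to detect a real interaction, and the likelihood of at least one chance signal across the seven factors. The SAP should say so beside the results, so that neither a significant nor a non-significant interaction is over-read.

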## 4.2 ANALYSIS SETS

The primary analysis will be based on the Intent-to-Treat (ITT) analysis set defined as all randomized subjects (based on study conduit group assignment).

The following rules will apply to the ITT analysis set:

- Subjects in whom the wrong conduit is implanted (e.g. an HAV implanted in a subject randomized to an ePTFE graft) will be analyzed within their randomized group rather than in their implanted group
- Subjects in whom no study conduit was implanted will be considered as if abandoned on Day 0 and included in their randomized group
- Subjects in whom the site (upper vs forearm) of implantation is different from the intended site will be analyzed based on the intended site.

The analysis will be repeated using the modified Intent-to-Treat (mITT) analysis set defined as all subjects in whom a study conduit has been implanted (based on actual conduit implanted and the actual site).

A secondary analysis will be conducted in a Per Protocol (PP) analysis set defined as all subjects in whom a study conduit has been implanted (based on actual conduit implanted) and in whom there were no major protocol deviations or data integrity concerns.

Major protocol deviations will be reviewed and verified at the time of determination, the time between the database soft lock and hard lock. Humacyte will identify major protocol deviation categories prior to the close of the database for the primary, second and final analysis. An overall major protocol deviation listing will be reviewed just prior to database lock for final analysis. Humacyte will approve all final major protocol deviation determinations. The protocol deviations SAS dataset will then be generated but will not be entered into the database.

Safety analysis will be conducted using the safety analysis set, which is defined as all subjects who receive study treatment, with the subject's treatment group based on the treatment that was received.

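### SAP 6.5 builds its subgroup models on the actual arm location, against the SAP's own ITT rule of analysing by intended site, and names no analysis set

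*SAP*

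**What the plan says.** SAP 6.5 plans subgroup analyses by region, gender, race, ethnicity, actual surgical location, age and BMI. They are done by "repeating the statistical methods described above for loss of secondary patency and loss of primary patency for each subgroup". One departure from the main analysis is then stated, and it concerns the location covariate: "except that the models will be adjusted by the actual surgical placement location (upper arm, forearm". Section 6.5 does not say in which analysis set.

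The method being repeated is in SAP 6.1: a "Cox proportional hazards regression with treatment group and the surgical placement stratification variable as factors". On the population, the same section says: "The primary analysis will be in the ITT analysis set". The mITT and per-protocol sets are confirmatory repeats.

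SAP 4.2 sets two ITT rules that bear on this. On location: "Subjects in whom the site (upper vs forearm) of implantation is different from the intended site will be analyzed based on the intended site". On subjects who receive nothing: "Subjects in whom no study conduit was implanted will be considered as if abandoned on Day 0 and included in their randomized group". Actual location is the stated rule only in the mITT definition, which covers implanted subjects "based on actual conduit implanted and the actual site".

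**The concern.** Under Protocol 5.2 and SAP 3.2.1 the surgeon chooses upper arm or forearm, the vessels are exposed, and only then is the subject randomised. Protocol 2.4.3.5 states that investigators cannot be blinded. The intended site is therefore a baseline variable and the randomisation stratum. The actual site is realised when the conduit is placed, with the allocation known. Adjusting for it, or grouping by it, conditions on something that follows randomisation. SAP 4.2 foresaw that the two sites may differ and chose the intended one for ITT; SAP 6.5 reverses that choice without saying that the population changes.

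A second issue may follow. A randomised subject with no conduit may have no actual location on record. In the ITT analysis that subject is a Day 0 failure, but a model needing actual location could lose the subject. A subgroup hazard ratio would then rest on a different population from the ITT result beside which it is read.

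**Working it through.** SAP 6.5 states no figure on this point, so there is none to reproduce. The check sets the texts side by side and then illustrates the size.

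**1. Texts compared**

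| Place | Analysis set | Arm location used |
|---|---|---|
| SAP 6.1 main Cox model | ITT | Randomisation stratum |
| SAP 4.2 ITT rules | ITT | Intended site |
| SAP 4.2 mITT definition | Implanted subjects only | Actual site |
| SAP 6.5 subgroup models | Not named | Actual site, as covariate and as a subgroup |
| SAP 6.1.1 items c–f and h–k (by sex) | ITT as primary set | None named |

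SAP 6.5 agrees with the mITT rule and conflicts with the ITT rule. The sexes could also be analysed under two rules, one from SAP 6.5 and one from SAP 6.1.1.

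**2. When would never-implanted subjects be lost?** Three conditions must all hold: the SAP 6.5 models are run in ITT; actual location is missing for these subjects; incomplete rows are omitted. The SAP states none of the three. Protocol 8.2.4 records the conduit's location as part of documenting the implantation, and SAP 4.4 has no rule for a missing location.

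**3. Size if all three hold.** Assumptions: n per arm in the subgroup; 60% event-free in both arms among implanted subjects (the 12-month planning rate for ePTFE in SAP 11, borrowed for illustration); k never-implanted subjects, all HAV. Then

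S_HAV = (n − k)/n × 0.60, and HR ≈ log(S_HAV)/log(0.60).

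| n per arm | k | S_HAV | HR with Day 0 failures | HR without them |
|---|---|---|---|---|
| 50 | 1 | 0.588 | 1.04 | 1.00 |
| 50 | 2 | 0.576 | 1.08 | 1.00 |
| 50 | 4 | 0.552 | 1.16 | 1.00 |
| 175 | 1 | 0.597 | 1.01 | 1.00 |
| 175 | 2 | 0.593 | 1.02 | 1.00 |
| 175 | 4 | 0.586 | 1.05 | 1.00 |

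Simulated Cox fits (1,500 subgroups per setting, 20% deaths per year, 18 to 34 months of follow-up) gave 1.04 for k = 1 and 1.09 for k = 2 at 50 per arm, and 1.00 once these subjects were removed.

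The direction depends on the arm. With two in each arm of 50, both rates are 0.576 and the HR is 1.00 either way. With four in the ePTFE arm only, log(0.60)/log(0.552) = 0.86, so dropping them would work against HAV. With none, nothing changes.

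**4. Against the noise.** At 50 per arm:
- Annual rate of patency loss: −log(0.60) = 0.511.
- Annual death rate: −log(0.80) = 0.223, from the roughly 20% in SAP 6.1. The total is 0.734.
- Mean follow-up: 26 months (2.17 years), the midpoint of 18 to 34.
- Expected events: 100 × (0.511/0.734) × (1 − exp(−0.734 × 2.17)) ≈ 55.
- SE(log HR) ≈ √(4/55) = 0.27, so the 95% interval around 1.00 is exp(±1.96 × 0.27) = 0.59 to 1.70.

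A shift to 1.09 is log(1.09)/0.27 ≈ 0.3 standard errors.

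**5. The margin.** SAP 6.1 sets the margin at log(S − 0.1)/log(S), with S the ePTFE Kaplan-Meier rate. At S = 0.60 this is log(0.50)/log(0.60) = 1.357. With two never-implanted ePTFE subjects of 50, S = 0.576 and the margin is log(0.476)/log(0.576) = 1.346. The Kaplan-Meier estimate needs no location covariate. Outside the location subgroups, these subjects could therefore count in the margin but not in the hazard ratio compared with it. The numerical effect is small, but the two quantities would rest on different subjects.

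**The case against.** SAP 6.5 introduces actual location with explicit wording of exception, so it is a prespecified choice and not a slip. If the authors meant these analyses for mITT, actual site is the rule there and never-implanted subjects are excluded by definition. Site is chosen and vessels are exposed before allocation, and the conduits are alike in size (6 mm by about 42 cm against 6 mm by 40 cm), so a change of site after allocation is probably uncommon. No switching rate is given. If actual and intended sites nearly always agree, the choice of covariate barely matters. The subgroups carry no confirmatory claim.

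Most of this stands as a limit on size. It does not remove the conflict: SAP 6.5 says it repeats methods whose primary set is ITT, and it does not announce a move to mITT.

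A reader might go further and infer that never-implanted subjects drop out of all subgroup results. The documents do not support that:
- It needs the three unstated conditions above. Since randomisation follows vessel exposure, an operated site may well be on record even when nothing was implanted.
- The sex-specific analyses in SAP 6.1.1 name no actual-location covariate, and Kaplan-Meier estimates outside the location subgroups need none.
- Few such subjects are likely. SAP 6.1.1 allows that the mITT set may not differ from the ITT set.

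A reader might also infer a bias towards HAV. That requires the never-implanted subjects to be mainly in the HAV arm, which nothing in the documents indicates.

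**Conclusion.** The conflict is established from the text and needs no assumption: the SAP 6.5 subgroup models and the location subgroup use actual location, while SAP 6.1 and the SAP 4.2 ITT rule use the randomised or intended one. Using a variable settled after an unblinded allocation is avoidable here.

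The loss of Day 0 failures from the subgroup Cox models is a possibility, not a finding. If it occurs, its size depends on how many subjects were never implanted and in which arm; the documents give neither. The illustrative shift from 1.00 to about 1.04 to 1.09 puts one or two such subjects in the HAV arm of a single subgroup of 50 per arm, and it lies well inside the sampling error. The effect of switching site was not quantified, for want of a rate.

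The primary analysis and the fixed testing sequence in SAP 6.2 are untouched. This is a free improvement in clarity and consistency, not a threat to the trial's conclusion.

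**What to change.** In SAP 6.5:

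- State that the subgroup analyses are done in the ITT set.
- For those analyses, use the intended (randomised) arm location both to define the location subgroup and as the model covariate.
- Use actual location only in mITT and per-protocol repeats.
- Omit the location covariate within the location subgroups, where it is constant and therefore redundant.

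This takes two or three sentences. The stratum was recorded at randomisation, so no new data are needed. Every ITT subject then stays in the subgroup models, including any with no conduit, and SAP 6.5 agrees with SAP 4.2 and 6.1.
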